5.0 Analysis Populations

- Enrolled Population: All participants who sign informed consent.
- Randomized Population: All participants who are randomized, analyzed as per randomized treatment.
- Modified intent-to-treat (mITT) Population: All participants who are randomized and receive at least 1 dose of study treatment, analyzed according to randomized treatment. All primary efficacy analyses will be conducted using this population.
- As Treated (Safety) Population: All participants who are randomized and receive at least 1 dose of study medication, analyzed according to treatment actually received. This population will be essentially the same as the mITT unless a participant received an incorrect treatment, i.e., a treatment different from what he/she was randomized to. All safety analyses will be conducted using this population.

6.0 Statistical Methods

6.1 Efficacy Analyses

All efficacy analyses, both primary and secondary, will be performed on the Modified-Intent-to-Treat (mITT) population, unless otherwise specified.

6.1.1 Primary Efficacy Analysis

The primary efficacy endpoint is the proportion of participants who achieve a ≥ 1 -stage improvement (as defined by NASH CRN Fibrosis Score) in fibrosis without worsening of NASH or NASH improvement (as defined by NAFLD Activity Score) with no worsening of fibrosis (as defined by NASH CRN Fibrosis Score) at Week 24, as determined by liver biopsy.

For this protocol, improvement in fibrosis is defined as a decrease of fibrosis by ≥ 1 point, as determined by the NASH CRN Fibrosis Score. Worsening of fibrosis is defined as an increase of fibrosis by ≥ 1 point, as determined by the NASH CRN Fibrosis Score. Worsening of NASH is defined as an increase of the

Sponsor: Bristol-Myers Squibb

Protocol no: MB130-068

NAFLD Activity Score (NAS) by ≥ 1 point. NASH improvement is defined as a decrease of NAS by ≥ 2 points (with contribution from > 1 NAS component).

A Cochran-Armitage trend test of proportions at a one-sided 0.05 level of significance will be used to examine the linear trend among the proportions across treatment groups. In addition, 95% confidence intervals (CIs) for the odds-ratio of each BMS treatment group to placebo will be provided. The null hypothesis states that there is no association between treatment groups and fibrosis stage improvement. The alternative hypothesis states that there is an association between treatment groups and fibrosis stage improvement. The Cochran-Armitage trend test does not take into consideration stratification factors into the model therefore, further sensitivity analysis will be performed as described below in SAP Section 6.1.1.1.

The proportion of participants with response will be summarized as frequency counts and percentages by randomized strata as well as overall for each treatment group.

Participants who prematurely discontinue from treatment without a biopsy result for NASH CRN Fibrosis Score or NAS at Week 24 (or ET, if applicable) or otherwise have a missing Week 24 (or ET, if applicable) biopsy result will be considered non-responders for the primary analysis of the primary efficacy endpoint.

The primary analysis will be based on the mITT population. In addition, a completer analysis of the primary variable will be performed. Patients with an evaluable Week 24 biopsy results are considered completers. All biopsy results will be included in the participant listings.

6.1.1.1 Sensitivity Analyses

There will be a sensitivity analysis of primary efficacy endpoint to determine the effect of the stratification variables Japan, T2DM and NAS using the randomized strata. A sensitivity analysis using an extended Cochran Mantel-Haenszel (CMH) correlation test will be used to assess the trend among the proportions for treatment groups with an adjustment to strata. A two-sided 0.10 level of significance will be used. In addition, logistic regression analysis will be performed to further assess the dose response relationship with treatment groups and stratification factors as main effects.

6.1.2 Secondary Efficacy Analyses

All secondary efficacy analyses will be based on the mITT population using the same methodology as the primary efficacy analysis. Since this is a Phase 2 study, no adjustment for multiplicity will be applied. The p-values will be considered descriptive.

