8.3.1 Inclusion Criteria

1. Signed written informed consent
 - a) Participants must be willing to participate in the study and sign the informed consent form(s) (ICF[s])
 - b) Participants (and caregivers as applicable) must be willing and able to complete all study-specific procedures and visits
2. Liver biopsy performed within 6 months (26 weeks) prior to the Screening Period. Biopsy performed prior to ICF must be available to the central reader prior to randomization. If historical biopsy is not available, a liver biopsy will be performed during the Screening Period (see [Section 8.5.1.1](#)). Biopsy must be consistent with NASH, with:
 - a) A score of at least 1 for each NAS component (steatosis, lobular inflammation, and ballooning), as assessed by the central reader
AND
 - b) Stage 3 liver fibrosis according to the NASH CRN classification, as assessed by the central reader
3. Participants taking anti-diabetic, anti-obesity, or anti-dyslipidemic medications must have been on stable regimens for at least 3 months (12 weeks) (6 weeks for statins) prior to and during the Screening Period. The investigator may contact the medical monitor regarding the stability of a participant's regimen when determining eligibility for study participation. Participants taking vitamin E at doses ≥ 800 IU/day must have been on stable doses for at least 6 months (26 weeks) prior to and during the Screening Period. Vitamin E treatment (≥ 800 IU/day) must not have been initiated after the qualifying liver biopsy was performed.

4. Age and reproductive status
 - a) Men or women 18 to 75 (inclusive) years of age
 - b) Women of childbearing potential (WOCBP) must have a negative pregnancy test (minimum sensitivity 25 IU/L or equivalent units of human chorionic gonadotropin) within 24 hours prior to the start of study medication
 - c) Women must not be breastfeeding at any time during the study
 - d) WOCBPs must agree to follow instructions for method(s) of contraception for the duration of treatment (BMS-986036 or placebo) plus 5 half-lives of study medication (5 days) plus 30 days (duration of ovulatory cycle) for a total of 35 days after the end of the Double-Blind Treatment Period
 - e) WOCBPs who are continuously not heterosexually active are exempt from contraceptive requirements but must undergo pregnancy testing as described in the Schedule of Activities in [Section 1](#)

[figure not shown]

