9.5.2.3 Methods for Handling Treatment Discontinuations and Other Causes of Missing Data

Participants who prematurely discontinue study medication will be expected to complete an ET Visit and must continue to be followed for follow-up visits/procedures per the Schedule of Activities (e.g., Week 52/PTFU) (see [Section 1](#)).

Primary efficacy analyses will include all data that are collected on a participant during the study even after treatment discontinuation. All efficacy analyses will be performed with the mITT population, analyzed according to randomized treatment.

Additional details for handling of missing data will be provided in the SAP.

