4.2 Secondary Efficacy Endpoints

The secondary efficacy endpoints are the proportion of participants with the following:

- NASH CRN Fibrosis Score $>=1$ stage improvement at Week 24
- Ishak Score $>=1$ stage improvement at Week 24
- Any CPA decrease at Week 24
- NASH resolution (NAS component of ballooning = 0 and inflammation = 0-1) without worsening of fibrosis (as defined by NASH CRN Fibrosis Score) at Week 24
- NASH resolution (NAS component of ballooning = 0 and inflammation = 0-1) at Week 24
- NASH improvement (reduction of NAS by ≥ 2 points with contribution from > 1 NAS component) without worsening of fibrosis at Week 24
- Achieve a ≥ 1 -stage improvement (as defined by NASH CRN Fibrosis Score) in fibrosis without worsening of NASH
- NASH improvement (reduction of NAS by ≥ 2 points with contribution from > 1 NAS component) at Week 24
- Progression to cirrhosis (as defined by NASH CRN Fibrosis Score) at Week 24

Sponsor: Bristol-Myers Squibb

Protocol no: MB130-068

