6.4 Exploratory Analyses

Analyses for exploratory endpoints will be performed using the mITT or safety populations.

Exploratory dichotomous response variables will be summarized in a manner similar to that used for the secondary efficacy analyses. In addition, summaries of ≥ 1 stage improvement, no change, and worsening will be tabulated and graphically presented for NASH CRN Fibrosis Score, Ishak Fibrosis Score, and NAS Total at Week 24. For these analyses, participants without a Week 24 or ET result will be classified into the "Worse" category for these exploratory summaries.

Early termination visits for non-biopsy endpoints such as imaging and biomarkers may occur at other time points and will not be summarized together with Week 24. For non-biopsy endpoints, ET will be summarized separately in the summary tables. Imputation on missing data will not be performed for non-biopsy endpoints.

Summary statistics will be tabulated for all treated subjects by treatment and by Visit. Continuous data will be summarized using n, mean, standard deviation, median, minimum, and maximum.

Analysis of covariance (ANCOVA) model will be used to explore change from baseline for endpoints having a baseline and a post-baseline values.

Repeated measures analysis will model the change from baseline for the endpoint in presence of repeated measurements taken at various timepoints on/before the analysis visit.

Sponsor: Bristol-Myers Squibb

Protocol no: MB130-068

The model will include treatment group, visit, baseline value, treatment * visit and baseline stratification factors as main effects. An unstructured covariance matrix will be used to represent the correlation of the repeated measures within each subject. The model will provide point estimates, standard errors and 2-sided 95% confidence intervals for mean change from baseline at by time points.

Other biomarkers will be descriptively summarized by time point and will include percent change from baseline in addition to change from baseline. Exploratory endpoints assessing relationships will be graphically presented.

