8.6 Liver Biopsy Scoring

Histological assessment of the liver tissue sample will be conducted by a blinded Central Pathologist. The central reader will be a medical doctor, board certified in pathology, with experience in liver pathology in a clinical study setting. Additional details on the acquisition, quality requirements, histological preparation, and shipping of histological samples are in the Central Laboratory Manual and the Central Pathology Manual or Charter.

Histological Scoring

NASH CRN

For associated primary and secondary endpoints, the NASH CRN system will be used to score the histologic samples and results are reported as the NAFLD Activity Score (NAS) and the NASH CRN Fibrosis Score. The NASH CRN system is based on the concept that necroinflammatory lesions and stage of fibrosis should be evaluated separately; it assesses liver biopsies for degree of steatosis (0-3), lobular inflammation (0-3), hepatocellular ballooning (0-2), and fibrosis (0-4).

Sponsor: Bristol-Myers Squibb

Protocol no: MB130-068

NAS

The 3 categories of steatosis, lobular inflammation, and ballooning scores are added together in an unweighted fashion to determine the NAS, which ranges from 0 to 8 (see table below).

Histology Variable	Grade	Score
Steatosis	< 5%	0
	5%-33%	1
	> 33% - 66%	2
	> 66%	3
Lobular Inflammation ^a	none	0
	< 2	1
	2 - 4	2
	> 4	3
Ballooning	none	0
	few	1
	many	2

NAS = NAFLD Activity Score

^a Foci per x200 field

Fibrosis

NASH CRN Fibrosis

Fibrosis is staged separately from NAS on a 0-4 scale: 0 (none); 1 (perisinusoidal or periportal fibrosis); 2 (perisinusoidal and portal/periportal fibrosis); 3 (bridging fibrosis); 4 (cirrhosis).

Participants will be evaluated for progression to cirrhosis (NASH CRN Fibrosis stage 3 to stage 4) at Week 24.

Ishak

A modified Ishak scoring system will also be used to stage fibrosis in the histologic samples. The Ishak system (0-6 scale) was originally developed to grade portal-based liver fibrosis associated with viral hepatitis. The modified Ishak system has been adapted to stage central-based liver fibrosis associated with NASH, and it also uses a 0-6 scale:

- 0: No fibrosis
- 1: centrilobular pericellular fibrosis
- 2: centrilobular and periportal fibrosis
- 3: bridging fibrosis (few bridges)
- 4: bridging fibrosis (many bridges)
- 5: early or incomplete cirrhosis
- 6: established or advanced cirrhosis

Sponsor: Bristol-Myers Squibb

Protocol no: MB130-068

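### If SAP 6.1.2 carries the primary missing-biopsy rule over to progression to cirrhosis, a missing biopsy is scored as not progressed, the favourable value on a harm endpoint

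*SAP*

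**What the plan says.** SAP 6.1.2 governs all nine secondary endpoints: "All secondary efficacy analyses will be based on the mITT population using the same methodology as the primary efficacy analysis". It adds that there is no multiplicity adjustment and that "The p-values will be considered descriptive". It does not mention missing biopsies.

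Eight of the endpoints in SAP 4.2 count a favourable result. The ninth is "Progression to cirrhosis (as defined by NASH CRN Fibrosis Score) at Week 24". SAP 8.6 gives its meaning: "Participants will be evaluated for progression to cirrhosis (NASH CRN Fibrosis stage 3 to stage 4) at Week 24".

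The only missing-biopsy rule in the primary methodology is in SAP 6.1.1. Participants with a missing Week 24 or ET "biopsy result will be considered non-responders for the primary analysis of the primary efficacy endpoint". That section also plans a completer analysis, named for the primary variable.

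SAP 6.4 has a second rule. In the improved / no change / worse summaries of NASH CRN fibrosis, Ishak fibrosis and NAS, "participants without a Week 24 or ET result will be classified into the" Worse category. The rule is limited to those exploratory summaries. Protocol 8.3.1 requires every participant to enter with "Stage 3 liver fibrosis according to the NASH CRN classification, as assessed by the central reader".

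Protocol 9.5.2.2 applies the primary approach to secondary endpoints unless the SAP specifies otherwise. Protocol 9.5.2.3 adds "All efficacy analyses will be performed with the mITT population, analyzed according to randomized treatment" and leaves further missing-data detail to the SAP.

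**The concern.** Treating a missing biopsy as non-response is conservative when response is the good outcome, because a participant without data earns no credit. When the counted event is harm, the same coding works in reverse: being left out of the numerator is the good result. Nothing in the SAP defines a responder for progression to cirrhosis, and nothing exempts the endpoint from the carried-over method.

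Two things are at stake. The reported progression rate would be too low whenever biopsies are missing, and an arm with more missing biopsies would look slightly better for that reason alone. Also, one participant could appear as Worse in the exploratory fibrosis table and as not progressed in the secondary table, although for someone starting at stage 3 these describe the same event.

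**Working it through.** **The plan's own figures.** The plan states no progression rate and no missing-biopsy rate, so there is no figure of its own to reproduce for this endpoint. The nearby power statement (at least 80%, SAP 2.2) concerns the primary endpoint. It reproduces: 86.8% at 40 per arm, one-sided 0.05, equally spaced scores. It does not bear on this point.

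**Inputs.** From the documents: about 40 per arm (160 planned, and approximately 160 in the Week 24 analysis, SAP 7.2) or about 49 per arm (197 randomized). Assumed: q = 5–15% progression among evaluable biopsies, m = 5–20% of biopsies missing, and missingness unrelated to outcome. Two provisions reduce m: ET biopsies after Week 20 (Protocol 8.5.1.1) and inclusion of delayed biopsies up to Week 48 (SAP 7.2). Before Week 20 an ET biopsy is only to be considered.

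**Formulas for one arm.**
- Missing = not progressed (SAP 6.1.1 rule carried over): q(1 − m)
- Missing = progressed (matches the Worse category in SAP 6.4): q(1 − m) + m
- Evaluable biopsies only: q

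**Understatement under the carried-over rule.** q − q(1 − m) = q × m.
- Lowest: 0.05 × 0.05 = 0.25 percentage points
- Middle: 0.10 × 0.10 = 1 point
- Highest: 0.15 × 0.20 = 3 points

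**Worked counts.**

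| Arm | Not progressed | Progressed | Evaluable only |
|---|---|---|---|
| 40 participants, 4 missing, 4 progressions | 4/40 = 10.0% | 8/40 = 20.0% | 4/36 = 11.1% |
| 49 participants, 5 missing, 4 progressions | 4/49 = 8.2% | 9/49 = 18.4% | 4/44 = 9.1% |

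**Active/placebo odds ratio with no true effect, q = 10% in both arms.** Example at 5% missing on placebo and 12% on active:
- Not progressed: rates 0.095 and 0.088, so (0.088/0.912)/(0.095/0.905) = 0.92.
- Progressed: rates 0.145 and 0.208, so (0.208/0.792)/(0.145/0.855) = 1.55.

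| Missing, placebo / active | Not progressed | Progressed | Evaluable only |
|---|---|---|---|
| 10% / 10% | 1.00 | 1.00 | 1.00 |
| 5% / 12% | 0.92 | 1.55 | 1.00 |
| 12% / 5% | 1.09 | 0.65 | 1.00 |
| 5% / 20% | 0.83 | 2.29 | 1.00 |
| 20% / 5% | 1.21 | 0.44 | 1.00 |

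In participants, the 5% / 12% case under the carried-over rule is 40 × (0.095 − 0.088) = 0.28 of an expected event per arm.

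**Trend test.** This was simulated (200,000 trials per setting) with 49 per arm, equal q of 10–20% in every arm, and missingness rising from placebo to 40 mg as 5/10/15/20% or 5/10/20/30%. These assumptions reach beyond the ranges above. The chance of a false one-sided 0.05 trend towards less cirrhosis is 8–18% under missing = not progressed and about 5% with evaluable biopsies. Under missing = progressed, the chance of a false trend towards more cirrhosis is 39–88%.

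**When imputed cases outnumber observed ones under missing = progressed.** m > q(1 − m), that is m > q/(1 + q): 4.8%, 9.1% and 13.0% at q = 5, 10 and 15%.

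**The case against.** The strongest reply is that the carry-over is contestable. The SAP 6.1.1 rule is worded for the primary endpoint, so reading SAP 6.1.2 as importing no missing-data rule is about as literal. Both explicit missing-biopsy rules (SAP 6.1.1 and 6.4) assign the unfavourable result, so the likely intent is not to credit missing biopsies. If the same methodology also brings the completer analysis with it, the evaluable rate would be produced anyway. Table conventions may sit in the separate shell document. The understatement is small, equal missingness leaves the odds ratio at 1.00, p-values are descriptive, and observed stage changes appear in the shift tables (SAP 4.5) and the listings (SAP 6.1.1). SAP 7.2 describes the Week 24 efficacy data as covering participants with a completed biopsy. If that limits the analysis set, m is about 0 there and the issue does not arise; but the same sentence also invokes the mITT principle.

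Most of this stands, and it limits the size of the point. It does not remove it. SAP 6.1.2 positively applies the primary method to every secondary endpoint, and the programmer is left with a rule that gives the wrong direction for one of them.

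A reader might infer three stronger things that the documents do not support.
- That the SAP states missing = not progressed. It does not; this follows only if the rule is carried over.
- That missing = progressed is the required main analysis. SAP 6.4 confines its Worse rule to exploratory summaries. Protocol 9.5.2.3 sets the population and does not call for imputing progression.
- That the drug will look better. That needs more missing biopsies on active treatment, and no document gives missing rates by arm.

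**Conclusion.** The concern holds in a limited form: as written, the method carried over by SAP 6.1.2 misfires on progression to cirrhosis, and the severity is minor. If applied, it scores missing biopsies as not progressed, at odds with SAP 6.4. Over the assumed q and m the rate is understated by 0.25 to 3 points, and the odds ratio moves to 0.92 or 0.83 with no true effect (q = 10%) when active arms miss 12% or 20% against 5% on placebo. What is affected is the secondary rate, its odds ratios and a descriptive p-value.

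Making missing = progressed the headline would replace a small bias with a larger one in the opposite direction (1.55 against 0.92 in the same setting). The evaluable-biopsy rate is the better main figure. It is unbiased only if missingness is unrelated to outcome, which is why the imputed rate is still worth showing.

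**What to change.** Add to SAP 6.1.2:

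> For progression to cirrhosis, a missing Week 24/ET biopsy is not counted as non-progression. The rate and odds ratios are reported among mITT participants with an evaluable Week 24/ET biopsy, with the number missing per arm. Missing = progressed (as in SAP 6.4) is reported as a sensitivity analysis.

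Protocol 9.5.2.2 allows the SAP to specify such an exception. Protocol 9.5.2.3 should not be cited as support for the imputation. The SAP 6.4 convention can stay as it is.

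The cost is a few sentences, the missing counts and one sensitivity row. The downside is that the main rate for this endpoint no longer uses the full mITT denominator; the sensitivity row keeps that denominator in view.

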6.2 Safety Analyses

6.2.1 Adverse Events

All adverse events will be presented based on the safety population by treatment group, and pooled BMS-986036.

A summary of treatment-emergent AEs, including the number of events reported and the number and percentage of participants reporting

- at least one AE
- any severe AE
- any treatment-related AE
- any AEs of special interest
- any severe treatment-related AE
- any AE with outcome of death

Sponsor: Bristol-Myers Squibb

Protocol no: MB130-068

- any serious AE
- any treatment-related SAE
- any AE leading to the discontinuation of study treatment
- any treatment-related AE leading to the discontinuation of study treatment
- any AE leading to discontinuation of the study
- any treatment-related AE leading to discontinuation of the study

A breakdown of the number and percentage of participants reporting each AE, categorized by system organ class (SOC) and preferred term (PT) will be presented. Maximum severity will be summarized for all TEAE by SOC and PT. Counts for AEs will be by participant not event and participants are only counted once within each SOC or PT.

Only treatment-emergent AEs will be summarized in tables. All AEs will be included in listings. In addition DILI will be presented graphically.

6.2.2 Deaths and Serious Adverse Events

A summary of treatment-emergent SAEs, categorized by SOC and PT will be presented. Counts will be by participant, not event, and participants are only counted once within each SOC or PT. All treatment-emergent SAEs and all SAEs will be listed.

Treatment-emergent AEs with an outcome of death will be summarized by SOC and PT. All treatment-emergent AEs with an outcome of death will be listed.

6.2.3 ECGs, Vital Signs, and Physical Examinations

Based on the safety population, vital sign and 12-lead ECG parameters will be summarized by visit, treatment group, and pooled BMS-986036. All vital signs and ECG results will be listed.

ECG results will be summarized for continuous variables and will be presented for the absolute result and change from baseline. QTcF (QT interval corrected using Fridericia's formula) values will be presented with the implementation of corrections (i.e., Fridericia's) as defined in ICH Guidelines E14 by the following categories:

Absolute QTcF interval prolongation:

- o QTcF interval > 450ms
- o QTcF interval > 480ms
- o QTcF interval > 500ms

Change from baseline in QTcF interval:

- o QTcF interval increases from baseline >30ms
- o QTcF interval increases from baseline >60ms.

Physical examination results and other safety data will be listed.

